4.8.7 Missing Data

Most data collection will be via online questionnaires (i.e., at T0, T2, T3, T4, and T5), which provide opportunities for preventing and monitoring missing data. We will offer other formats for questionnaire completion (including paper and standardized interviews), thus minimizing missing data. We will prompt each patient, by telephone (or email at Dartmouth), to complete the follow-up questionnaires (i.e., T3, T4, and T5) or reach them in the clinic during their post-surgery appointments. Given the brevity of the trial and the procedures described above, we do not anticipate more than 5% of missing data. However, should there be more than a trivial amount of missing data, we will use multiple imputation to cope with missing baseline, interim, and outcome data. We will record and report all reasons for dropout and missing data. Multiple imputation creates multiple completed data sets by drawing random values of missing outcome or predictor variables from the predictive distribution of these variables given the observed variables¹⁴². This approach will address both generalizability and causal validity bias. We will also examine sensitivity of inferences.

4.8.8 Heterogeneity of Treatment Effects

The main goals of the heterogeneity of treatment effects (HTE) analyses are to estimate treatment effects in clinically relevant subgroups and to predict whether an individual might benefit from exposure to the decision aid. As the HTE analyses are exploratory rather than hypothesis-driven, exploratory subgroup analyses will be conducted to identify hypotheses for future evaluation. Patient characteristics will be considered for treatment by covariate interactions and include SES, age, ethnicity, race, literacy, language, and study site¹⁴³. As described in the analytic plans for testing interactions by SES in Aims 1 and 2, interaction tests will be conducted to determine if subgroup analyses of the intervention effects by the levels of that predictor are warranted. If the interaction is significant, then the treatment effect is estimated separately at each level of the categorical variable used to define mutually exclusive subgroups.

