4.1.2 Randomized Controlled Superiority Trial (Aims 1 and 2)

According to Cooper et al., the most appropriate design for evaluating interventions that aim to eliminate disparities is a classic experimental design with random assignment to experimental and control groups, with measurements of key variables pre- and post-interventions⁸². We have thus chosen to conduct a three-arm, multi-site randomized controlled superiority trial with stratification by SES (high versus low) and randomization at the clinician level (nested within study sites) (see Fig. 5).

Fig. 5. CONSORT* Study Flow Diagram

*CONSORT stands for Consolidated Standards of Reporting Trials, as reported in the CONSORT statement⁸⁷.

At each site, we will use a cross-sectional study design and randomize participating clinicians (three to five clinicians per site) to one of three arms (Picture Option Grid, Option Grid, or usual

care). We will use an R script written by the study statistician to complete the surgeon randomization. At each site, patients who have given informed consent and are seeing one of the participating clinicians will be allocated to the clinician's corresponding arm (Picture Option Grid, Option Grid, or usual care). Approximately the same number of patients in each socioeconomic stratum will be allocated to each arm. We will monitor accrual within each arm for each socioeconomic stratum at each site to ensure that a similar number of patients in each socioeconomic stratum receive each treatment. The total number of patients recruited at each site will be allowed to vary.

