4.7.5 Randomization

Randomization will be at the clinician level, nested within study sites. We will use an R script written by the study statistician for randomization of the surgeons. The statistician will be blinded to surgeon identification. At each site, patients who have given informed consent and are seeing one of the participating clinicians will be allocated to the clinician's corresponding arm (Option Grid, Picture Option Grid, or usual care).

Approximately the same number of patients in each socioeconomic stratum will be allocated to each arm. We will monitor accrual within each arm for each socioeconomic stratum at each site to ensure that each arm has a similar number of patients in each socioeconomic stratum. The total number of patients recruited at each site will be allowed to vary.

In the intervention conditions, each participant whose eligibility has been confirmed by the surgeon during the consultation will be given a copy of the Option Grid or Picture Option Grid by their surgeon and will use it in the clinic visit.

In the usual care condition, the patients will receive care as usual and will be given a study card at the end of the consultation to signal to the research assistant or patient associate that the patient has been enrolled into the study.

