4.8 Analysis

4.8.1 Power Calculation

For Aim 1, hypothesis 1, we base the effect size estimation on published data from randomized controlled trials of decision aids for breast cancer surgery^{32,41,115,116}, suggesting that a reasonable effect size for DQI is 9.34, that the standard deviation between patients in the intervention arms compared to usual care is 12.00, and that a within-physician intra-class correlation (ICC) of 0.05 is reasonable. This ICC is justified because treatment varies within clinic, thereby allowing heterogeneity that occurs between physicians across centers to be blocked. We assume that four physicians will participate in the study at each of the four clinics (at least one assigned to each of the three trial arms at each center) and assume a patient attrition rate of 20%. Under these assumptions, a study of 1,100 participants (68.75 participants per physicians and 366.66 per treatment group) has power of greater than 99.8%

to reject the null hypothesis that the encounter decision aid groups and the control group have equal means, using a two-sided 0.05 level test when the true mean difference is 9.34. Given recruitment difficulties due to seasonal trends in breast cancer diagnoses and a lower number of eligible patients than planned based on the feasibility assessments (see reasons in modification letter), the sample size has been revised to 600 participants. The power will remain above 80% for all primary hypotheses.

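### Section 4.8.8 tests arm by study site and, if significant, estimates arm effects within sites, although a site's arm is often one surgeon and no surgeon-level error rule is given

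*Combined protocol and SAP*

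**What the plan says.** Section 4.8.8 names seven covariates for interaction with treatment: "Patient characteristics will be considered for treatment by covariate interactions and include SES, age, ethnicity, race, literacy, language, and study site". The follow-on rule is the same for all seven: "If the interaction is significant, then the treatment effect is estimated separately at each level of the categorical variable". The section qualifies the work: "As the HTE analyses are exploratory rather than hypothesis-driven".

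On the design, section 4.7.5 says "Randomization will be at the clinician level, nested within study sites", and section 4.1.2 gives "three to five clinicians per site" for three arms. The power calculation in section 4.8.1 takes four surgeons per site, with "at least one assigned to each of the three trial arms at each center".

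Section 4.8.3 adopts a regression framework for all analyses and says that nesting of patients in professionals, and of professionals in sites, will be handled by mixed models or generalized estimating equations (GEE). Neither 4.8.3 nor 4.8.8 gives a small-sample rule for degrees of freedom. Neither treats study site differently from the patient-level covariates.

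**The concern.** Age, race, literacy and the other patient-level covariates can vary within one surgeon's caseload, so their interactions with arm can draw on differences between patients of the same surgeon. Site cannot vary within a surgeon. It is the block in which surgeons are randomised, and an arm effect inside one site rests on a handful of surgeons, often one against one.

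Two things follow. The arm-by-site test has very few surgeon-level degrees of freedom, so the usual large-sample inference rejects too often. And whatever the test, the within-site estimates that follow a significant result carry surgeon differences that the data at that site cannot remove. At stake is an exploratory finding that an aid seems to work better at one center than another, when the data may show only that two surgeons differ.

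**Working it through.** **Inputs.** From 4.8.1: SD 12, ICC 0.05, difference 9.34, attrition 20%, two-sided 0.05, revised N 600, four surgeons at each of four sites. From 4.1.2: three to five surgeons per site. Assumed: equal patients per surgeon, and an ICC range of 0.01 to 0.19 (0.19 is a sensitivity value in 4.8.1; 0.01 is my lower bound).

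**The plan's own figure.** With N = 1,100 there are 1,100 × 0.8 / 3 = 293.3 per arm and 1,100 × 0.8 / 16 = 55 per surgeon. Design effect = 1 + 54 × 0.05 = 3.70. Effective n = 79.3 per arm, SE = 12 × √(2/79.3) = 1.906, and 9.34/1.906 = 4.90. Power = Φ(4.90 − 1.96) = 0.998, which agrees with the stated value. The plan gives no power or error rate for arm by site.

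**Surgeons per arm at a site.**
- Three surgeons: 1-1-1, so all three arms are a single surgeon.
- Four: 2-1-1, so two of three are.
- Five: 2-2-1 (one of three) or 3-1-1 (two of three).

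**Degrees of freedom.** Four sites × three arms = 12 cell means, and the interaction has 3 × 2 = 6 df. Surgeon-level df = surgeons − 12: 0, 4 or 8 with 12, 16 or 20 surgeons.

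**Surgeon noise in a one-against-one contrast.** Surgeon variance = 0.05 × 144 = 7.2 (SD 2.68). The SD of a difference between two surgeons is √(2 × 7.2) = 3.79, which is 41% of 9.34, with a 95% range of ±7.4. More patients do not reduce it.

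**Precision within a site.** With 600 × 0.8 / 16 = 30 patients per surgeon, SE = √[2 × (7.2 + 136.8/30)] = 4.85, against √(2 × 144/30) = 3.10 if surgeon is ignored. The 95% half-width is 2.776 × 4.85 = 13.5 points on the pooled 4 df, and 12.706 × 4.85 ≈ 62 points on the single df inside one site. Both exceed 9.34.

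**False positive rate of the 6-df test.** No true site heterogeneity, 480 analysed, ICC 0.05, by simulation:

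| Surgeons per site (patients each) | Surgeon ignored | Surgeon random effect, large-sample Wald | Surgeon-level F |
|---|---|---|---|
| 3 (40) | 66% | not separable | not available (0 df) |
| 4 (30) | 54% | 20% | 5%, F(6,4) |
| 5 (24) | 45% | about 14% | 5%, F(6,8) |

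Across ICC 0.01 to 0.19 with four per site, the first rate runs from 14% to 95%, the second from 8% to 25%, and the third stays at about 5%.

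**GEE.** When the model fits the mean of a single-surgeon cell, that surgeon's residuals sum to zero and the cell adds nothing to the robust variance. With four per site, only the four two-surgeon cells contribute, one dimension each. The robust covariance then has rank 4, too low for a 6-df Wald test, and the robust SE of a one-against-one contrast is zero.

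**The case against.** The strongest reply is that section 4.8.3 commits all analyses to models that account for surgeon, and 4.8.8 does not depart from it. That stands. A reader might infer from the 54% that the planned test would be wrong more than half the time, but that rate belongs to an analysis ignoring surgeon, which the plan does not specify. With surgeon as the error unit the test holds its 5% level, and the within-site step would then seldom be triggered when there is no heterogeneity. What does not stand is that 4.8.3 is enough as written: without a df rule, the usual mixed-model test still gives about 20%, and the robust GEE test cannot be computed.

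A reader might also infer that most site-by-arm cells are always a single surgeon. That fails for a 2-2-1 split of five. Nor is the test always impossible: that holds only when every site has three surgeons.

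A further stronger reading is that the trial would conclude that an aid works at one center and not at another. The documents do not support it: the analysis is labelled exploratory, is meant to generate hypotheses, and gives site effects only after a significant interaction.

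Finally, section 4.4.3 says that usual-care resources differ across sites, so there is a real reason to look at site. This argues against banning any site analysis. It does not make the within-site estimates interpretable.

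**Conclusion.** The point holds as a correction to one exploratory analysis. Under the plan's assumption of four surgeons per site and ICC 0.05, the arm-by-site test rejects falsely about 20% of the time with the surgeon random effect and large-sample inference (about 14% with five per site), and holds 5% only with a surgeon-level small-sample test. With three per site, no model can separate site-by-arm effects from surgeon. At any of these counts, a within-site arm effect depends heavily on a few surgeons: surgeon variation alone gives a one-against-one contrast an SD of 3.8 points.

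The figures rest on equal caseloads, the plan's SD and 480 patients analysed; the rates move with the ICC as shown. The main cross-site arm comparison is not affected.

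**What to change.** In section 4.8.8, take study site out of the rule that tests an interaction and then estimates the effect at each level, and keep site in the models as the block term. Report site-by-arm results descriptively, with the number of surgeons and the surgeon-level means in each cell, and make no site-specific effect claim. If an arm-by-site test is kept because usual care differs by site, state that surgeon is the error unit, that small-sample degrees of freedom are used, and that the test is omitted when no surgeon-level df remain.

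Align the heterogeneity lists in the scientific abstract (section 1.2) and in the abstracts attached to Appendix E-1, Appendix E-2 and the DSMB charter (Appendix F).

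The cost is a few lines of wording. One low-powered exploratory analysis is lost or becomes descriptive.

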4.8.9 Access to the Dataset

Only the statistician and core research team will have access to the final data set. All data used in conducting the final analysis of the randomized controlled trial will be made available to PCORI in a de-identified copy for archival purposes in no more than nine months from the end of the final analysis. We will also provide a strategy for making de-identified subsets of data for collaborating researchers and organizations within nine months of completion. We also plan to develop a Data Access, Analysis, and Expression of Interest submission and review process for formal requests to make use of the data so as to prevent

duplication in analysis and publication. Given the data sharing plans, we will provide a detailed description of these plans to all participants during the informed consent process to ensure that participants are aware of all potential uses of data.

4.9 Data Management

Data management for the study will be done through REDCap, a HIPAA-compliant web-based data management system. REDCap will be hosted at Dartmouth-Hitchcock Medical Center for data collected at DHMC. Data collected from all other sites will be hosted on REDCap at Dartmouth College. REDCap is designed to support data capture for research studies, providing 1) an intuitive interface for validated data entry; 2) audit trails for tracking data manipulation and export procedures; 3) automated export procedures for seamless data downloads to common statistical packages; and 4) procedures for importing data from external sources¹⁴⁴. Access will only be granted to study team members designated to manage the study data and will require a dedicated username and password. Study team members with access at participating study sites will only have access to the data at their corresponding institution. This database management system is designed to comply with the ICH Good Clinical Practice (GCP) guidelines.

Data entry into REDCap will be done by research assistants and patient associates at each site using standardized data collection forms. Samples of the data collection forms will be available once they are finalized.

In addition, each study site will have a data-protected, encrypted external hard drive for the local storage of sensitive study-related materials. Each of the study sites will return the hard drives to Dartmouth College at the end of the trial. Dartmouth will store the encrypted data for six years after the conclusion of the trial, after which all data will be destroyed. No personally identifiable data will be transferred or stored outside of REDCap and encrypted hard drives.

Signed consent forms will be kept in a locked file cabinet in a secure location at each study site and kept for six years after the conclusion of the trial.

4.9.1 Data and Safety Monitoring Plan

A Data and Safety Monitoring Board (DSMB) will be appointed to provide additional oversight in the trial. The DSMB will meet and review data bi-annually throughout the project. The DSMB will include key stakeholders in the participating communities (one patient representative and breast surgeon) as well as academics with expertise in statistics, patient engagement in health care, breast cancer surgery, and health disparities. The DSMB will operate independently from the study sponsor.

The DSMB will review the protocol, data collected to date, advise the PI on any potential risks and risk mitigation plans. The DSMB recommendations will be discussed with the PI as well as the Trial Steering Group, which meets quarterly (see section 7.2). Those recommendations will also be fed back to PCORI every six months as part of the bi-annual reports. The Trial Steering Group will consider all DSMB recommendations and revise relevant aspects of the trial accordingly. All data will be reviewed for protocol adherence, including a data verification check that the appropriate outcome measures are given at the appropriate time points.

We do not expect any Serious Adverse Events (SAE) or Adverse Events (AE) in the trial that would require immediate reporting. There are no invasive procedures related to the interventions. However, some patients, particularly those with diagnosed mental illness or patients who are finding it difficult to cope with their recent cancer diagnosis, may find it stressful to be randomized to one of the two encounter decision aids or to usual care. All members of the research and medical care team who are involved in patient recruitment and follow-up assessments will be asked:

- Ahead of recruitment: To identify available counseling/psychological support. This information will be included in the cover letter and information sheet;
- During recruitment: To refer participants (who are distressed as a result of participating in the trial) to relevant counseling/psychological support services;
- During recruitment: To remind the participant that she is free to withdraw from the trial at any time without providing any reason;
- During recruitment: To notify the study PI of any participants who are withdrawing from the trial because of psychological distress or anxiety directly related to trial participation.
- During recruitment: All research assistants and patient associates will know who to refer patients to when patients have clinical questions or need additional information or support.

In addition, during each DSMB meeting, the DSMB will review data on subject withdrawals from the study and will be provided with the stated reason for withdrawal and the study subject anxiety score (measured PROMIS) for each withdrawal.

If for any reason, an SAE or AE were reported to the Principal Investigator (PI), the IRB at Dartmouth would be immediately notified as well as the appropriate safety board at the participating sites. The DSMB would convene urgently and review the SAE/AE.

5 Write-up and Dissemination

5.1 Dissemination and Implementation in Other Settings

This study is highly relevant to patient-centered care as we seek to promote the involvement of women of low SES in breast cancer treatment decisions and address disparities in this area. Currently, women of low SES are more likely to make treatment decisions based on incomplete or uninformed preferences, potentially leading to poor decision quality, poorer quality of life, and decision regret. This study hopes to identify solutions that effectively improve outcomes across socioeconomic strata and reduce disparities in quality of care (Aim 1 and 2). Addressing the current disparity in care based on SES requires effective dissemination of the results, maximizing implementation potential, and embedding these protocols into routine care (Aim 3)

It is often a challenge to bridge the gap between health research and health action and to effectively communicate results of studies to practicing clinicians, policy-makers, and patients. By dedicating a full 12 months of this project to this aim, we hope to successfully change the way shared decision-making is implemented in breast cancer treatment and provide better accessibility to women of lower SES. The study outputs will likely interest a wide variety of target audiences, ranging from patient and advocacy groups, healthcare professionals, and healthcare organizations, to academics, policy makers, and decision aid developers. This diverse group of audiences will maximize the potential for implementation and dissemination. We will work with each target audience to create dissemination and implementation strategies that are tailored to their needs and interests, understandable, and pertinent to them. Since the interventions are easily accessible and inexpensive to update and disseminate, implementation in routine care could occur immediately post-project completion. We plan to disseminate findings through the following various channels.

5.1.1 Academic Channels

Although peer-reviewed scientific journals are not commonly accessed by patients, it remains the primary source of knowledge and dissemination of research findings to influence health professionals, policy makers, and healthcare organizations. These channels will be used to ensure that clinicians have access to the study findings and are able to rapidly and successfully implement the intervention(s) in routine clinical settings. In order to promote access to patients and other non-academic stakeholders, we will publish all study outputs in open-access journals. Recently, some journals (i.e., New England Journal of Medicine) have begun including a short video abstract alongside the article. We will try to publish in academic journals with this video functionality with the aim of making the material accessible to a broader audience.

Given the vast amount of information available, many clinicians do not have time to keep up with all research literature and instead focus on clinical practice guidelines¹⁴⁵. We hope that recommendations arising from this study about optimal ways to engage patients of low SES in breast cancer surgery decisions can be incorporated into clinical practice guidelines at the participating institutions and beyond.

We will also present the findings at up to four domestic and international scientific conferences (e.g., International Shared Decision Making Conference) and professional meetings to promote wider dissemination of the study findings. We hope to do a pre-conference workshop in order to train clinicians using interactive role-play and instructive videos (replicating the training of physicians in our study). It is our hope that these dissemination activities will be enhanced through networking and have a ripple effect where workshop participants will return to their own workplaces and integrate the use of successful intervention(s) into clinical practice.

